1.2 Schedule of Events

Table 1: Screening Schedule of Events

Procedure	Screening Visit	Notes
Eligibility Assessments		
Informed Consent	X	Register in IRT system to obtain patient number. Must occur prior to any protocol-specific study assessments
Inclusion/Exclusion Criteria	X	Must be confirmed prior to randomization
Medical History	X	Assessment of signs and symptoms and all medical history, including smoking history and alcohol use
Cancer History	X	Summary of melanoma cancer history, including prior treatment and BRAF mutation status (local results, if available)
Review of Pathology Report and Staging	X	Investigator documents staging and complete resection of disease (complete resection must be performed within 12 weeks prior to randomization) and provides pathology report for Sponsor review (refer to Inclusion Criterion No. 4 in Section 4.1)
Imaging Assessments	X	Within 28 days prior to randomization (see Section 7.3) Contrast-enhanced CT of the chest; contrast-enhanced CT or MRI of the abdomen, and pelvis and all known sites of resected disease Brain MRI (without and with contrast) (head CT with contrast allowed if MRI contraindicated and if there is no known history of treated brain lesions) Ultrasound of sentinel-node basin
Tumor Tissue Sample	X	Tumor tissue from biopsy or resected disease must be available and sent to a central laboratory: formalin-fixed paraffin-embedded block or unstained slides. Central PD-L1 classification ($\geq 1\%$, $< 1\%$, indeterminate, or not evaluable) required for randomization. Please refer to Section 5.8.1 for further details.

Procedure	Screening Visit	Notes
Safety Assessments		
Full Physical Examination	X	Within 14 days prior to randomization (see Section 8.17)
Vital Signs	X	Within 14 days prior to randomization Blood pressure, pulse, respiratory rate, temperature, pulse oximetry, height, and weight (see Section 8.18)
Performance Status	X	Within 14 days prior to randomization (see Appendix 3)
Prior and Concomitant Medication Use	X	Within 14 days prior to randomization (see Section 5.13) Document vaccine use within 30 days prior to randomization
Clinical Laboratory Testing	X	Within 14 days prior to randomization Laboratory assessment of hematology, chemistry, urinalysis, and serology (see Appendix 1)
Pregnancy Test	X	Within 14 days prior to randomization (see Section 8.13) Serum or urine test (minimum sensitivity 25 IU/L or equivalent units of HCG) in WOCBP

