Overall, 1.9% (26 of 1345) of patients exposed to bempegaldesleukin reported CVA events. Of the 26 patients, 13 patients experienced Grade 3 or 4 events and 4 patients had a fatal outcome. The mean time to first CVA event was 218.7 days (range 4 to 727 days; median 158 days). Twenty of the 26 patients with CVA events received a doublet combination with a checkpoint inhibitor, which included 1.7% (19 of 1116) of patients who received nivolumab, 1.3% (1 of 76) who received pembrolizumab, and 0% (0 of 23) who received atezolizumab.

Based on these events, CVA was escalated to an adverse event of special interest (AESI) and mitigations were put in place to reduce the risk of CVA. These mitigations include implementation of a CVA adverse event management algorithm ([Appendix 6](#)) and updates to the exclusion criteria, renal function and hydration assessment, hydration guidelines, concomitant and prohibited medications, dose modification guidelines, and discontinuation criteria. Additional information on the clinical safety and risk of CVA is found in the bempegaldesleukin Investigator's Brochure.

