5.12.1 Discontinuation Criteria for Treatment-Related Toxicities

Patients meeting any of the following criteria will be required to permanently discontinue all assigned study drug(s). In Arm A, per Investigator assessment, treatment with bempegaldesleukin or nivolumab alone may continue if a toxicity meeting discontinuation criteria below is considered related to one and not the other study drug and once the criteria to resume treatment are met (Section 5.10.3).

Study treatment should be permanently discontinued for the following:

- Any Grade ≥ 2 treatment-related uveitis, eye pain, or blurred vision that does not respond to topical therapy and does not improve to Grade 1 severity within 8 weeks or requires systemic treatment.
- Any Grade ≥ 2 treatment-related pneumonitis or interstitial lung disease that does not resolve following dose delay and systemic steroids (also see Pulmonary Adverse Event Management Algorithm in the nivolumab Investigator's Brochure).
- For Grade ≥ 3 adrenal insufficiency or Grade ≥ 4 hypophysitis, treatment needs to be discontinued regardless of control with hormone replacement (Note: Hospitalization for diagnostic workup of adrenal insufficiency without severe symptoms should not require discontinuation).
- Any Grade ≥ 3 non-skin, treatment-related AE lasting > 7 days or recurs, with the following exceptions for uveitis, pneumonitis, bronchospasm, diarrhea, colitis, neurologic toxicity, hypersensitivity reactions, infusion reactions, endocrinopathies, and laboratory abnormalities:
 - Grade 3 treatment-related uveitis, pneumonitis, bronchospasm, diarrhea, colitis, neurologic toxicity, hypersensitivity reaction, or infusion reaction of any duration requires discontinuation.
 - Grade 3 treatment-related endocrinopathies (excluding adrenal insufficiency and hypophysitis) adequately controlled with only physiologic hormone replacement do not require discontinuation.
 - Grade 3 treatment-related laboratory abnormalities do not require treatment discontinuation except:
 - Grade 3 treatment-related thrombocytopenia > 7 days or associated with clinically significant bleeding requires discontinuation.

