- In most cases of Grade 3 AST or ALT elevation, study treatment will be permanently discontinued. If the Investigator determines a possible favorable benefit/risk ratio that warrants continuation of study treatment, a discussion between the Investigator and the Medical Monitor/designee must occur. For IL-2 mediated ALT/AST elevations $< 8.0 \times \text{ULN}$ in Cycle 1 only, study treatment does not need to be discontinued (see Section 5.10.2).

- Any treatment -related liver function test abnormality that meets the following criteria require discontinuation (also see Hepatic Adverse Event Management Algorithm in the nivolumab Investigator's Brochure):
 - AST or ALT $> 5 \times$ ULN to $8 \times$ ULN for > 2 weeks
 - AST or ALT $> 8 \times$ ULN
 - Total bilirubin $> 5 \times$ ULN
 - Concurrent AST or ALT $> 3 \times$ ULN and total bilirubin $> 2 \times$ ULN
- Grade 3 or 4 infusion reaction of any duration:
 - For Arm A: If infusion reaction occurs during the bempegaldesleukin infusion or prior to the nivolumab infusion, discontinuation of bempegaldesleukin is required.
 - For Arm A: If infusion reaction occurs during the nivolumab infusion or later, discontinuation of both bempegaldesleukin and nivolumab is required.
- Any Grade 4 treatment -related AE or laboratory abnormality, except for the following events, which do not require discontinuation:
 - Grade 4 neutropenia ≤ 7 days.
 - Grade 4 lymphopenia or leukopenia ≤ 14 days in duration.
 - Isolated Grade 4 amylase or lipase abnormalities that are not associated with symptoms or clinical manifestations of pancreatitis and decrease to Grade < 4 or return to baseline within 7 days.
 - Isolated Grade 4 electrolyte imbalances/abnormalities that are not associated with clinical sequelae and are corrected with supplementation/appropriate management within 72 hours of their onset.
 - Grade 4 treatment -related endocrinopathy AEs (except adrenal insufficiency or hypophysitis), such as hyper- or hypothyroidism, or glucose intolerance, which resolve or are adequately controlled with physiologic hormone replacement (corticosteroids at ≤ 10 mg of prednisone or equivalent per day, thyroid hormones) or glucose-controlling agents, respectively, may not require discontinuation after discussion with and approval from the Medical Monitor.
- Any AE, laboratory abnormality, or intercurrent illness that, in the judgment of the Investigator, presents a substantial clinical risk to the patient with continued treatment.

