- Arm A only: Any new CVA event confirmed by diffusion-weighted imaging MRI, regardless of neurological symptoms (e.g., cryptogenic CVA) and for suspected TIA without clear alternative etiology (see [Appendix 6](#))

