APPENDIX 5: CORTICOSTEROID DOSE EQUIVALENTS

Equivalent Dose	Steroid
1.2 mg	Betamethasone
1.5 mg	Dexamethasone
8 mg	Methylprednisolone
8 mg	Triamcinolone
10 mg	Prednisone
10 mg	Prednisolone
40 mg	Hydrocortisone
50 mg	Cortisone

[Mager, 2003; Webb, 2005](#)

APPENDIX 6: CEREBROVASCULAR ACCIDENT ADVERSE EVENT MANAGEMENT ALGORITHM FOR THE COMBINATION OF BEMPEGALDESLEUKIN WITH CHECKPOINT INHIBITORS

The table below provides a management algorithm for possible signs/symptoms of CVA for patients treated with the combination of bempegaldesleukin with a checkpoint inhibitor. This general guideline constitutes guidance to the Investigator and may be supplemented by clinical judgment of the Investigator and/or discussions with the Medical Monitor representing the Sponsor.

For unexplained neurological symptoms (such as hemiparesis, confusion, dysarthria, or visual disturbances) that may be associated with CVA:	

 • Recommend following the Advanced Cardiac Life Support (ACLS) Adult Suspected Stroke Algorithm that includes time-sensitive assessment and rtPA use guidance^a. • Perform neurological imaging with DWI MRI as soon as feasible after the initial presentation of symptoms, preferably within 24 hours, or as indicated following an acute intervention. DWI MRI is preferred, but if contraindicated, alternative imaging modalities may be used. 	
If imaging is consistent with a CVA, proceed to the following:	
1	For any new CVA event confirmed by imaging (DWI MRI preferred unless contraindicated), regardless of neurological symptoms (eg, cryptogenic CVA), and for suspected TIA without clear alternative etiology: 
 • Discontinue study treatment for patients receiving bempegaldesleukin in combination with a checkpoint inhibitor (ie, nivolumab).
2	Neurology consultation recommended.
3	Perform pertinent laboratory assessments including coagulation (D-dimer, complete blood count with differential, serum blood urea nitrogen, and creatinine) [REDACTED]
4	Consider cardiac echocardiogram (trans-esophageal as appropriate) to evaluate for potential source of emboli.

CVA = cerebrovascular accident; DWI = diffusion-weighted imaging; MRI = magnetic resonance imaging; rtPA = recombinant tissue plasminogen activator; TIA = transient ischemic attack.

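### The mandatory Arm A stroke-stopping rule in Section 5.12.1 names only diffusion-weighted MRI as confirmation, while Appendix 6, which it cites, accepts other imaging when MRI is contraindicated

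*Protocol*

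**What the plan says.** Section 5.12.1 of the Protocol opens by stating that patients who meet any listed criterion must permanently stop all assigned study drugs. The last bullet, for Arm A only, covers "Any new CVA event confirmed by diffusion-weighted imaging MRI, regardless of neurological symptoms". It adds suspected TIA with no other clear cause and refers to Appendix 6. It names no other imaging method.

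Step 1 of Appendix 6 directs that treatment be discontinued: "For any new CVA event confirmed by imaging (DWI MRI preferred unless contraindicated), regardless of neurological symptoms". Its work-up instruction adds: "DWI MRI is preferred, but if contraindicated, alternative imaging modalities may be used". Appendix 6 describes itself as guidance that the Investigator's clinical judgment may supplement.

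On entry, Table 1 (Section 1.2) allows screening brain imaging by CT: "head CT with contrast allowed if MRI contraindicated and if there is no known history of treated brain lesions".

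**The concern.** This is one rule written twice with different conditions. The CVA bullet in the mandatory list is narrower than the algorithm it cites, and the wider version sits in text that calls itself guidance.

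The difference matters for an Arm A patient who cannot have MRI and whose stroke is confirmed by CT or another method. Read literally, the Section 5.12.1 bullet does not apply to that patient, while Appendix 6 says to stop. The TIA clause needs no imaging, but a confirmed infarct is not a suspected TIA.

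CVA is the only adverse event of special interest listed in Section 8.10. Among the 26 pooled CVA patients in Section 2.1.3.2.5.2, "13 patients experienced Grade 3 or 4 events and 4 patients had a fatal outcome". That section names both the Appendix 6 algorithm and revised discontinuation criteria as mitigations, so the two should agree.

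**Working it through.** The plan gives no figure of its own on this point. The check is a comparison of the two texts, followed by a rough size.

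**Comparison**

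| Element | Section 5.12.1 | Appendix 6, step 1 |
|---|---|---|
| Event | any new CVA | any new CVA |
| Confirmation | diffusion-weighted MRI | imaging; diffusion-weighted MRI preferred unless contraindicated |
| Symptoms needed | no | no |
| Suspected TIA, no other clear cause | included | included |
| Action | permanent discontinuation | discontinue |

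The difference at issue is the means of confirmation.

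**Can the affected patient exist?** Yes. Table 1 admits patients with an MRI contraindication who have no known treated brain lesions. Table 2 allows head CT on treatment for patients without baseline brain metastases when MRI is contraindicated, and for patients with treated brain lesions who develop a contraindication during the study.

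**Which other criteria in Section 5.12.1 stop treatment without MRI?**

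- Grade 3 treatment-related events: "neurologic toxicity, hypersensitivity reaction, or infusion reaction of any duration requires discontinuation".
- Any Grade 4 treatment-related event, with listed exceptions that do not include stroke.
- Any event that, "in the judgment of the Investigator, presents a substantial clinical risk to the patient with continued treatment".

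The first two need both grade and relatedness, and the third needs a judgment. A stroke that is Grade 1-2 or judged unrelated is left to judgment or to Appendix 6. Relatedness is a real filter: in the initial PIVOT-02 analysis (Section 2.1.3.2.5.1), Investigators judged the CVA events related to at least one study treatment in 4 of the 9 affected doublet patients.

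**Size: inputs**

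- CVA rate with the doublet (Section 2.1.3.2.5.2): "1.7% (19 of 1116) of patients who received nivolumab".
- Planned Arm A size: 475 (Section 9.2).
- Share unable to have MRI: 2-10%, an assumption because the documents give no figure.
- Grade 1-2 share among the 26 pooled CVA patients. If the 4 fatal cases are separate from the 13 with Grade 3 or 4 events, (26 - 13 - 4)/26 = 9/26 = 0.346. If they are among the 13, (26 - 13)/26 = 13/26 = 0.50. Applying this share to the doublet is also an assumption.

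**Size: results**

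- Expected Arm A patients with a CVA: 475 x 19/1116 = 8.09.
- Of these, unable to have MRI: 8.09 x 0.02 = 0.16 to 8.09 x 0.10 = 0.81.
- Grade 1-2 only, lower share: 8.09 x 0.346 = 2.80; x 2-10% = 0.06-0.28.
- Grade 1-2 only, upper share: 8.09 x 0.50 = 4.04; x 2-10% = 0.08-0.40.
- Overall Grade 1-2 range: 0.06-0.40 patients. Higher-grade strokes judged unrelated could add to this.

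**The case against.** The strongest reply is that the bullet cites Appendix 6, so an Investigator who follows the reference finds the wider rule. On that reading the bullet is only a short form, and nothing in it says that a patient with a CT-confirmed stroke may continue. This lowers the risk but does not remove the conflict, because the reference leads to a different condition in a text that calls itself guidance.

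A second reply is that the mandatory list is itself partly discretionary, since Section 5.12.1 lets an Arm A patient continue one drug if the toxicity is attributed only to the other. That is true, and it softens the contrast between the two texts. It does not change what counts as a confirmed stroke.

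Third, there are further safeguards. Section 5.12 stops treatment when the Investigator thinks continued participation is against the patient's interest. Section 5.10.1.2 delays both drugs in Arm A for a Grade 2 treatment-related non-skin event. Section 8.10 brings every CVA to the sponsor within 24 hours. These help, but the first rests on judgment, the second is only a delay, and the third is a reporting rule.

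Fourth, the size is probably overstated. Section 2.1.3.2.5.2 includes onsets up to 727 days, against about one year of treatment here, and it describes mitigations introduced because of those events. The 0.2-0.8 range also counts fatal strokes, for which a stopping rule is moot. These points stand and push the estimate down.

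Finally, the SAP (Sections 2.0 and 5.1) records that the programme was ended on 14 April 2022 and the study terminated. A correction therefore has limited practical use now, though the inconsistency in the text remains.

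**Conclusion.** The inconsistency is real and of low severity. Section 5.12.1 requires a narrower confirmation than the algorithm it cites, and the trial admits patients for whom the difference matters. Fewer than one Arm A patient is expected to be affected: 0.2-0.8 on the bullet's wording alone, or 0.06-0.40 counting only Grade 1-2 events. These ranges rest on the assumed 2-10% unable to have MRI, on the earlier doublet CVA rate carried over unchanged, and, for the second range, on the pooled grade split. Reporting of CVA as an event of special interest is unaffected, because Section 8.10 covers any grade with no imaging condition. No endpoint, sample size or analysis changes.

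**What to change.** In the Arm A bullet of Section 5.12.1, replace the diffusion-weighted MRI condition with the one in Appendix 6, so that the bullet applies to any new CVA confirmed by imaging, with diffusion-weighted MRI preferred unless contraindicated. Keep the rest of the bullet as it is, including the TIA clause and the reference to Appendix 6. The cost is one sentence in a protocol amendment or clarification letter. It uses wording the sponsor has already adopted and adds no procedure.

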5.13 Prior and Concomitant Medications

Recording of prior medications should include prior cancer treatments, previous radiation, and over-the-counter medications.

All medications (prescription and over-the-counter), vitamin, and/or subsequent anticancer therapy taken by the patient from Screening through Follow-up Visit 2 visit will be documented and recorded, including start and stop date, dose and route of administration, frequency, and indication. Medications taken for a procedure (e.g., biopsy) should also be included. All medications taken to treat an AE/SAE should be recorded through Follow-up Visit 2.

Details regarding IV hydration will be recorded.

5.13.1 Prophylaxis and Management of Symptoms Related to Immediate Infusion-Related Reactions (Including Flu-Like Symptoms and Hypersensitivity Events)

Prophylaxis for flu-like symptoms with either acetaminophen or ibuprofen is permitted on study per the Investigator's discretion. Prophylaxis for flu-like symptoms should be initiated on either Day 1 or Day 2 of the dosing cycle and may continue through Day 5 or longer as needed.

Prophylaxis for rash and/or pruritus with antihistamines is permitted on study per the Investigator's discretion. Prophylaxis for rash and/or pruritus should be initiated on either Day 1 or Day 2 after dosing of bempegaldesleukin or nivolumab and may continue through Day 5 or longer as needed.

5.13.2 Permitted Concomitant Medications

5.13.2.1 Effect of Bempegaldesleukin on Concomitant Medications

At the study dose levels, bempegaldesleukin is expected to cause mild to moderate increases in circulating cytokines, some of which are known to have the potential to decrease the activity of multiple enzymes (cytochrome P450 enzymes, hepatic flavin monooxygenases, UDP-glucuronosyltransferases, sulfotransferases, and glutathione S-transferases) and drug transporters, and the suppressive effects can be additive (Haas, 2005; Zidek, 2009). The increases in circulating cytokines generally occur from Day 3 to Day 7 postdose, coinciding with the PK time course of bempegaldesleukin-related active cytokines (NKTR-214-AC). Consequently, treatment with bempegaldesleukin may lead to decrease in clearance of drugs that are substrates of these Phase 1 and Phase 2 drug metabolizing enzymes, or drug transporters, from Days 3 to 7 postdose. The magnitude of potential drug interactions with bempegaldesleukin is unknown. The clinical management of concomitant medications during the period of bempegaldesleukin-induced increases in cytokines is similar to treatment guidelines in the setting of an acute inflammatory response. That is, due to the possibility of broad reductions in clearance pathways, drugs with narrow therapeutic indices should be replaced with alternative agents that are not prone to drug interactions, reduced, or withheld

from Days 3 to 7 after administration of bempegaldesleukin. For further guidance, the investigator should consult with the Medical Monitor.

5.13.2.2 Steroids

Patients are permitted the use of topical, ocular, intra-articular, intranasal, and inhalational corticosteroids (with minimal systemic absorption). Patients with pre-existing adrenal impairment requiring corticosteroid supplementation may be at increased risk for hypotensive episodes during treatment with bempegaldesleukin. For these patients, their existing corticosteroid dose may be increased to adrenal replacement steroid doses > 10 mg of daily prednisone or equivalents for the first 4 days after administration of bempegaldesleukin based on an assessment of the degree of adrenal impairment and the extent of existing corticosteroid supplementation. A brief (less than 3 weeks) course of corticosteroids for prophylaxis (e.g., contrast dye allergy) or for treatment of non-autoimmune conditions (e.g., delayed-type hypersensitivity reaction caused by a contact allergen) is permitted. Use of corticosteroids for the management of immune-mediated AEs as outlined in the nivolumab Investigator's Brochure is permitted. Short-term use of systemic corticosteroids or immunosuppressive medication is permitted if administered for AE treatment. Daily dosage of prednisone or equivalents must be ≤ 10 mg for study treatment to resume.

5.13.2.3 Thromboembolism Prophylaxis and Treatment

Patients with a higher risk of thromboembolic event, or a history of venous or arterial thromboembolism must be receiving a stable regimen of anticoagulation. Low molecular weight heparin (LMWH) at prophylactic doses (e.g., enoxaparin at 1 mg/kg or flat dose up to 80 mg/day) is the preferred anticoagulant that should be initially considered. Other options such as oral factor Xa inhibitors (Direct Oral Anticoagulants) including rivaroxaban, apixaban, or edoxaban can be used after consulting with the Sponsor Medical Monitor. Unless there is a new medical contraindication observed after Cycle 1 Day 1, patients with a history of a venous or arterial thromboembolic event must be maintained on therapeutic anticoagulation throughout the time on study treatment. Acetylsalicylic acid should not be combined with LMWH or DOAC due to an increased risk of hemorrhage.

Warfarin is permitted; however, therapeutic dosing should target a specific international normalized ratio (INR) that is stable for at least 4 weeks prior to randomization. Reduction of warfarin dose after starting study treatment should be considered due to the possibility of drug-drug interactions between warfarin and bempegaldesleukin in which the latter has the potential to down-regulate metabolizing enzymes for warfarin. Frequent monitoring of INR and ongoing consideration of dose adjustments are warranted throughout the patient's participation on study, as bempegaldesleukin can down-regulate metabolizing enzymes for warfarin for approximately 1 week after administration of each dose of bempegaldesleukin.

